### 8.17.3 Assessment of Severity

The severity (or intensity) of an AE will be classified using the following criteria:

- Mild: These events are usually transient, require minimal or no treatment, and do not interfere with the subject's daily activities.
- Moderate: These events result in a low level of inconvenience or concern with the therapeutic measures. Moderate events may cause some interference with normal functioning but pose no significant or permanent risk of harm.
- Severe: These events interrupt a subject's usual daily activity and may require systemic drug therapy or other treatment. Severe events are usually incapacitating.

Changes in the severity of an AE should be documented as a new event to allow an assessment of the duration of the event at each level of intensity to be performed.

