## 3.4 Interim Analyses

This is an adaptive dose-response finding study.

Interim analyses will be conducted when data are available for approximately 40, 80 and 100 subjects in order for DMC to provide recommendation on the following:

- Omadacycline treatment group(s) that can be initiated or dropped from the trial
- Modification of the randomization ratios among the treatment groups
- Need for extension of the trial beyond 200 enrolled subjects to provide more precise estimates of the efficacy outcome

To protect the integrity of the clinical study, neither the actual randomization schedule nor the data from the data reviews will be made available to the Sponsor Study team or the Study Reporting team. Data for the unblinded data reviews by the DMC will only be released to the DMC, the independent reporting statistician, and the DMC Reporting team. For details refer to Data Monitoring Committee Charter for Phase II Trial for PTK0796-AP-17202.

Decisions on randomization re-allocation and/or dropping dose groups will be based primarily on safety and tolerability. Efficacy will only be considered for dose-reallocation if the DMC deems the response rates as too low to proceed with enrollment. Efficacy is not pre-planned with statistical decision criteria due to high variability in small sample sizes.

Based on the results of analyses during the interim reviews, the DMC may recommend continuation of enrollment above 200 subjects. The purpose of an increase in sample size, among other reasons, may be due to the need to provide more precise estimates of the efficacy outcome or for further exploration of safety and tolerability data.

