## 5.2 Definitions

In Table 2 general definitions are provided used in the statistical analysis.

Variable	Definition		
Baseline	Unless otherwise stated, baseline is defined as the value closest to but prior to the initiation of test article administration.		
Change from baseline	Change from baseline will be defined as the post-baseline value minus the baseline value (on a subject level). Change from baseline will only be calculated for subjects who have both baseline and at least one post-baseline value for any parameter.		
Duration Variables	Duration variables will be calculated using the general formula:		
	Duration (days) = End date - Start date + 1		
	If applicable, where time is collected:		
	Duration (hh:mm) = End datetime - Start datetime		
Calculated Creatinine Clearance (mL /min),	(140 – age [yrs]) * weight [kg] * Z	Z = 0.85 for Female subjects	
Cockcroft-Gault equation	Creatinine [mg/dL] * 72		
Body Mass Index (BMI)	$BMI = Weight (kg) / Height (m)^2$		

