## 8.4 Adverse Events

Adverse events (AEs) will be recorded and reported from signing of the ICF to the end of study. AEs will be coded using the MedDRA to the SOC and PT levels.

A treatment-emergent AE is defined as any AE that newly appeared or worsened in severity on or after the initiation of test article. An AE is considered treatment emergent if the AE start date and time is on or after the start date and time of the first dose of test article.

Summary tables will be provided for all treatment-emergent adverse events (TEAEs).

An overall summary of AEs will include the number of subjects who experienced at least one AE of the following categories: any AE, any TEAE, any drug-related TEAE, any severe TEAE, any serious TEAE, any drug-related serious adverse event, any serious TEAE leading to death, any TEAE leading to premature discontinuation of test article and any TEAE leading to premature discontinuation from study, and any serious TEAE leading to premature discontinuation of test article.

The number and percentage of subjects reporting a TEAE in each treatment group will be tabulated by SOC and PT. The incidence of serious TEAEs, TEAEs judged to be related to test article, TEAE leading to premature discontinuation of test article and from study will be summarized by SOC and PT. Additionally, a summary by SOC, PT, and severity (mild, moderate, and severe) will be provided. For all analyses of TEAEs, if the same AE (based on PT) is reported for the same subject more than once, the AE is counted only once for that PT and at the highest severity and strongest relationship to test article.

For the two omadacycline dose groups and the levofloxacin treatment group with the possibility to switch from iv to oral test article AEs will be summarized by incidence of subjects with events starting during iv treatment and events starting after the switch to oral treatment and combined for the total treatment group. This summary will be presented by SOC and PTs.

93 Version: 1.0 Status: Approved Approved Date: PTK0796-AP-17202 Statistical Analysis Plan

Omadacycline (PTK 0796)

Paratek Pharma, LLC

PTK0796-AP-17202 Statistical Analysis Plan

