In addition, all AEs (including non-TEAEs), serious TEAEs, and TEAEs leading to discontinuation of test article will be provided in listings by treatment group, study site, subject, verbatim term, MedDRA SOC and PT, start and end date, seriousness flag, severity, relationship to test article, relationship to study protocol, action taken with test article, non-test article action taken and outcome.

For subjects with a TEAE of nausea or vomiting (based on the MedDRA PT), the total number of nausea and vomiting events, descriptive statistics of the study day of first onset of these events, and descriptive statistics for the duration (in days) of events, will be presented by treatment group.

Listings of hospitalizations will be provided.

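### SAP 8.4 counts and times nausea and vomiting events without joining the separate records that the protocol opens at each severity change, so counts can be inflated and durations understated

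*SAP*

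**What the plan says.** **Recording.** Protocol 8.17.3 instructs sites: "Changes in the severity of an AE should be documented as a new event". The stated purpose is to let duration be assessed at each intensity. The rule covers changes in either direction.

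**Analysis.** For subjects with treatment-emergent nausea or vomiting, SAP 8.4 reports "the total number of nausea and vomiting events, descriptive statistics of the study day of first onset of these events", followed by "descriptive statistics for the duration (in days) of events, will be presented by treatment group". Event is not defined as a record or as an episode. There is no rule for joining records, and duration is not broken down by intensity. SAP 5.2 gives the formula "Duration (days) = End date - Start date + 1". SAP 5.1 lists the mean and the median among the summary statistics.

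**Count-once rule.** Earlier in SAP 8.4, a preferred term reported more than once in a subject is counted once, at its highest severity. The rule is worded to cover every analysis of treatment-emergent AEs (TEAEs).

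**Treatment emergence.** SAP 8.4 first defines a TEAE as one that is new, or has become more severe, once test article has started. The next sentence makes this operational by date alone, with initial dosing as the reference point: "An AE is considered treatment emergent if the AE start date and time is on or after the start date and time". SAP 5.3 repeats the date rule, and Protocol 12.6.1 also defines a TEAE by start date.

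**The concern.** The protocol splits records for one purpose, duration by intensity, and the SAP never uses them for it. Its nausea and vomiting summary uses counts and durations for which a split record is the wrong unit. An arm with more severity changes would show more events, each shorter than the episode it belongs to.

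Nausea and vomiting are the AEs of interest named in the protocol synopsis. The protocol's introduction (3.2) reports a higher than expected incidence of both in the earlier cystitis study. A duration summary that partly reflects how often severity was regraded is a poor basis for comparing regimens on these events.

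The date rule for treatment emergence has a related weakness. If an AE present before dosing improves afterwards, the recording rule produces a new, milder record that starts after the first dose. The date rule flags it; the definition one sentence earlier would not.

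**Working it through.** The plan states no figure to reproduce. The check applies the SAP 5.2 formula to hypothetical records. All episode lengths and split shares are assumptions, because the documents give none.

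**One episode.** Nausea runs from Day 2 to Day 6: severe on Days 2–3, moderate on Days 3–4, mild on Days 4–6, with adjoining records sharing a boundary date.
- Joined: 6 − 2 + 1 = 5 days, one event.
- By record: 3 − 2 + 1 = 2, 4 − 3 + 1 = 2, 6 − 4 + 1 = 3. That is three events with mean 7/3 = 2.3 days.

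**An arm in which a share f of 5-day episodes splits this way.** Records per episode are 1 + 2f. Recorded days per episode are 5(1 − f) + 7f = 5 + 2f. Mean record duration is therefore (5 + 2f)/(1 + 2f).

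| f | Events per 10 episodes | Mean record duration (days) |
|---|---|---|
| 0 | 10 | 5.0 |
| 0.2 | 14 | 5.4/1.4 = 3.9 |
| 0.5 | 20 | 6/2 = 3.0 |
| 1 | 30 | 7/3 = 2.3 |

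At f = 0.2 the count is 40% too high and the mean 23% too low (1 − 3.857/5). The median is still 5 days, because 8 of the 14 records are unsplit. Against an arm of unsplit 3-day episodes, the means reverse only when f exceeds 0.5.

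**Sensitivity to the assumed pattern.**
- Take 6-day episodes split into three 2-day records with no shared dates. The mean is 6/(1 + 2f): 4.3 days at f = 0.2, 3.0 at 0.5 and 2.0 at 1.
- With one severity change per 5-day episode, the two records total 6 days. Even if every episode splits, the mean is 6/2 = 3.0, a tie with the 3-day arm.
- Six days of nausea at constant severity give one record of 6 days and no bias.

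**Does the count-once rule repair this?** If it applied, the event total would only repeat the number of subjects per term. The SAP would still not say which record supplies the dates. Taking the highest-severity record in the first example gives 2 days for a 5-day episode, so duration remains understated.

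**Treatment emergence.** AEs are recorded from consent (Protocol 8.17). Screening falls within 24 hours before randomization and the first dose within 4 hours after it (Protocol 5.1). The pre-dose window is thus roughly 24 + 4 = 28 hours, so the contradiction can arise but only in a short interval.

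**The case against.** The SAP nowhere says that severity-change records are to be counted separately, and the count-once rule is worded broadly enough to cover this summary. That is fair: the text is in conflict rather than plainly wrong. Neither reading gives a sound duration, however.

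The damage is also limited. Subject incidence and the maximum-severity table are protected by the count-once rule, and day of first onset is unaffected when onset follows the first dose. The listings give start date, end date and severity, so episodes can be reconstructed. The summary is descriptive, with no test or criterion attached. All of this stands.

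On treatment emergence, the date rule matches Protocol 12.6.1, and nausea or vomiting before dosing may be treated as a qualifying sign of the infection rather than as an AE. This reduces the number of cases but does not remove the contradiction within SAP 8.4. Count-once cannot undo a falsely flagged record, because that record enters the incidence table itself.

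A reader might infer three stronger claims, which the documents do not support.
- **Splitting is greatest where nausea is most severe.** The trigger is a change of grade, not its level. Fluctuating mild-to-moderate nausea splits; constant severe nausea does not.
- **The worst-tolerated arm will appear to have the shortest nausea.** A reversal is arithmetically possible, but in the example it needs more than half of one arm's episodes split three ways and none in the other. The inflated count would meanwhile make that arm look worse.
- **Dose-group decisions rest on this table.** SAP 3.4 says "Decisions on randomization re-allocation and/or dropping dose groups will be based primarily on safety and tolerability", but SAP 3.5 places the SAP's analyses after the end of study. Interim content is left to the DMC charter, which is not among the documents.

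**Conclusion.** The point holds as a defect in how two descriptive summaries are specified, and it should be corrected. Followed literally, the plan inflates nausea and vomiting counts and understates durations in proportion to the number of severity changes recorded. In the illustration, splitting one episode in five gives 40% more events and a mean of 3.9 instead of 5 days, with the median unchanged. The size in this trial is unknown. It depends on how often grades change, how consistently sites apply Protocol 8.17.3, and whether the earlier record is closed when the new one opens, which the protocol does not state. If it is left open, the records overlap and still need joining. The direction by arm cannot be predicted.

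The conflict between the count-once rule and the event total does not depend on those assumptions, nor does the contradiction between the two TEAE sentences. The latter should affect few records.

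**What to change.** In SAP 8.4, with matching text in 5.3:

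1. Join contiguous or overlapping records of the same preferred term within a subject into one episode, with first start, last stop and maximum severity. State a gap rule, for example that at least one symptom-free day starts a new episode.
2. Count nausea and vomiting events as episodes and compute duration on episodes.
3. Show duration by severity level separately, from the unjoined records. This serves the purpose given in Protocol 8.17.3.
4. State that the count-once rule applies to the subject-incidence tables.
5. Do not flag as treatment-emergent a continuation record whose severity is the same as, or lower than, before the first dose. Because Protocol 12.6.1 uses start date alone, list this in SAP Section 9.

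The cost is SAP wording and a small programming step on data already collected. Nothing changes at sites.

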## 8.5 Clinical Laboratory Results

Clinical laboratory safety assessments include hematology (including coagulation), serum chemistry, and urinalysis.

Clinical laboratory parameters include those listed in the Appendix 1 Clinical Laboratory Tests (Central) and Local Urinalysis.

Baseline is defined as the central lab value closest to and prior to the first dose of test article. If no central lab value is available prior to the first dose of study drug, the local lab value that is closest to and prior to the first dose of study drug will be used as baseline. For by visit analyses, central lab values will be used unless no central lab value was obtained in the visit window. In this case, local lab values will be used for the by visit analyses. All lab values (central and local) are used for determination of the overall worst post-baseline value.

Laboratory data will be summarized by timepoint and for the overall worst post-baseline value using descriptive statistics (based on International System [SI] units) for the actual results and change from baseline for hematology and serum chemistry assessments.

Descriptive statistics (based on SI units) for chemistry, hematology and coagulation values and the change from baseline will be summarized by treatment group at each time point, and for the overall worst value post-baseline (which includes unscheduled visits).

Appendix 2 Directionality of Worst Laboratory Parameters provides the directionality of the worst values for each laboratory parameter.

Clinically notable laboratory values will be determined based on the Appendix 3 Modified Division of Microbiology and Infectious Diseases Adult Toxicity Table(DMID) criteria.

Shift tables will be presented to show the number of subjects with a laboratory value with a grade of 0, 1, 2, 3 or 4 at baseline versus the value at each visit. Number and percentage of subjects with at least a 2-grade increase from baseline (based on DMID criteria) will be summarized by treatment arm. Percentages for each laboratory test will be based on the number of subjects with a baseline and post-baseline evaluation of the specific laboratory test. A listing

93 Version: 1.0 Status: Approved Approved Date: PTK0796-AP-17202 Statistical Analysis Plan

Omadacycline (PTK 0796)

Paratek Pharma, LLC

PTK0796-AP-17202 Statistical Analysis Plan

will be provided for subjects who have at least a 2-grade increase from baseline in a given laboratory test.

The number and percentage (based on the number of subjects with a normal level at baseline) of subjects in each treatment group with an elevated transaminase level (> 3 × upper limit of normal [ULN], > 5×ULN, and > 10 × ULN), an elevated bilirubin level (> 1.5 × ULN and > 2 × ULN) will be presented by study visit. A listing of subjects who meet the laboratory criteria for Hy's law at the same visit will also be provided. The laboratory criteria for Hy's law is defined as 1) ALT or AST> 3 × ULN, ALP  $\leq$  2.0 × ULN, and total bilirubin > 1.5 ULN and 2) ALT or AST> 3 × ULN, ALP  $\leq$  2.0 × ULN, and total bilirubin > 2 × ULN

Tabulated results of urine dipstick tests for leukocyte esterase and nitrates will be summarized by treatment group across visits and will include descriptive statistics for the microscopic evaluations for white blood cells.

Subject listings of all laboratory data (local and central laboratory data) collected during the study will be provided, including calculated CrCl (using the Cockcroft-Gault equation). Laboratory values outside normal limits will be identified in the subject data listings with flags for low (L) and high (H) as will laboratory values that meet the clinically notable (CN) thresholds.

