  - Emphysematous pyelonephritis
  - Chronic pyelonephritis, including xanthogranulomatous pyelonephritis
  - Polycystic kidney disease
  - Renal carcinoma
13. History of renal transplant or a surgically created intestinal conduit for urinary diversion.
14. Suspected or confirmed non-renal source of infection (eg, prostatitis, epididymitis, orchitis, endocarditis, osteomyelitis, abscess, meningitis, pneumonia).
15. Confirmed or suspected vaginitis or sexually transmitted infection or lower UTI (ie, cystitis) without symptoms/signs of AP.
16. Has any of the following at Screening:
  - ALT or aspartate aminotransferase (AST)  $\geq 3 \times$  Upper Limit of Normal (ULN)
  - total bilirubin  $> 1.5 \times$  ULN
  - suspected or confirmed clinical evidence of end-stage liver disease (eg, ascites, hepatic encephalopathy)
17. History of unstable cardiac disease (eg, unstable angina, myocardial infarction, acute congestive heart failure, unstable cardiac arrhythmia, etc.) within the 3 months prior to randomization.
18. Significant immunological disease determined by any of the following:
  - Current or anticipated neutropenia defined as less than 500 neutrophils/mm^3
  - Known infection with Human Immunodeficiency Virus (HIV) and a cluster of differentiation 4 (CD4) count that is unknown or documented to be less than 200 cells/mm^3 within the last year, or other Acquired Immune Deficiency

- Syndrome (AIDS)-defining illness as determined by the investigator.
19. Receipt of cancer chemotherapy, radiotherapy, or potent, non-corticosteroid immunosuppressant drugs (eg, cyclosporine, azathioprine, tacrolimus, immune-modulating monoclonal antibody therapy, etc.) within the 3 months prior to randomization, or the receipt of systemic corticosteroids equivalent to or greater than 40 mg of prednisone per day (see equivalent corticosteroid doses in [Appendix 2](#)) or 40 mg of prednisone per day for more than 14 days in the 30 days prior to randomization.
  20. History of hypersensitivity or allergic reaction (eg, anaphylaxis, urticaria, other significant reaction) to any tetracycline (eg, minocycline, doxycycline or tigecycline) or fluoroquinolone (eg, levofloxacin, ciprofloxacin, moxifloxacin) antibiotic.
  21. Inability to swallow 6 tablets in succession.
  22. History of pseudotumor cerebri, or prior (within 2 weeks prior to randomization) or planned concomitant use of isotretinoin.

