  - Emphysematous pyelonephritis
  - Chronic pyelonephritis, including xanthogranulomatous pyelonephritis
  - Polycystic kidney disease
  - Renal carcinoma

13. History of renal transplant or a surgically created intestinal conduit for urinary diversion.
14. Suspected or confirmed non-renal source of infection (eg, prostatitis, epididymitis, orchitis, endocarditis, osteomyelitis, abscess, meningitis, pneumonia).
15. Confirmed or suspected vaginitis or sexually transmitted infection or lower UTI (ie, cystitis) without symptoms/signs of acute pyelonephritis.
16. Has any of the following at Screening:
  - alanine aminotransferase (ALT) or aspartate aminotransferase (AST)  $\geq 3 \times$  Upper Limit of Normal (ULN)
  - total bilirubin  $> 1.5 \times$  ULN
  - suspected or confirmed clinical evidence of end-stage liver disease (eg, ascites, hepatic encephalopathy)
17. History of unstable cardiac disease (eg, unstable angina, myocardial infarction, acute congestive heart failure, unstable cardiac arrhythmia, etc.) within the 3 months prior to randomization.
18. Significant immunological disease determined by any of the following:
  - Current or anticipated neutropenia defined as less than 500 neutrophils/mm^3
  - Known infection with Human Immunodeficiency Virus (HIV) and a cluster of differentiation 4 (CD4) count that is unknown or documented to be less than 200 cells/mm^3 within the last year, or other Acquired Immune Deficiency Syndrome (AIDS)-defining illness as determined by the investigator.
19. Receipt of cancer chemotherapy, radiotherapy, or potent, non-corticosteroid immunosuppressant drugs (eg, cyclosporine, azathioprine, tacrolimus, immune-modulating monoclonal antibody therapy, etc.) within the 3 months prior to randomization, or the receipt of systemic corticosteroids equivalent to or greater than 40 mg of prednisone per day (see equivalent corticosteroid doses in [Appendix 2](#)) or 40 mg of prednisone per day for more than 14 days in the 30 days prior to randomization.
20. History of hypersensitivity or allergic reaction (eg, anaphylaxis, urticaria, other significant reaction) to any tetracycline (eg, minocycline, doxycycline or tigecycline) or fluoroquinolone (eg, levofloxacin, ciprofloxacin, moxifloxacin) antibiotic.
21. Inability to swallow 6 tablets in succession.
22. History of pseudotumor cerebri, or prior (within 2 weeks prior to randomization) or planned concomitant use of isotretinoin.

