## 7.4 Dose Selection Rationale

The dosing regimen of omadacycline selected for this study is based on the nonclinical and clinical experience to date, including *in vitro* antibacterial activity, PK characteristics, clinical efficacy in prior studies, and the overall safety and tolerability profile. Key considerations in dose selection are summarized below:

- In PTK0796-SDES-0501, the PK of omadacycline iv were linear over the entire dose range (25 mg to 600 mg) as assessed by area under the concentration time curve (AUC). Therefore, the loading dose given on Day 1 in the pivotal Phase 3 trials, 100 mg iv every 12 hours (q12h), is from an exposure perspective comparable to the 200 mg iv loading dose on Day 1 to be utilized in this study.
- In PTK0796-MDES-0601, 200 mg iv for seven days was safe and well tolerated. Alanine aminotransferase was reported as increased in 26% of subjects however the post-baseline change was approximately 30 IU/L on the last day of infusion. A heart rate model demonstrated that the post-baseline increase in heart rate for a 200 mg dose could be minimized to 15 beats per minute with infusion over 60 minutes.
- In PTK0796-UUTI-15103, omadacycline dosed as 200 mg iv on Day 1 followed by 300 mg po daily for 5 days, 300 mg po q12h on Day 1 followed by 300 mg po daily for 5 days and 450 mg po q12h on Day 1 followed by 450 mg po daily for 5 days demonstrated high urinary concentration on Day 1 and Day 5. For the 200 mg iv load followed by 300 mg daily dosing group, mean urinary concentrations ranged from 22 to 65 µg/mL on Day 1 and 21 to 42 µg/mL on Day 5. For the 300 mg dosing group, mean urinary concentrations ranged from 14 to 20 µg/mL on Day 1 and 17 to 30 µg/mL on Day 5. For the 450 mg dosing group, mean urinary concentrations ranged from 11 to 25 µg/mL on Day 1 and 30 to 48 µg/mL on Day 5.

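### The liver threshold table in SAP 8.5 is based on subjects with a normal baseline, although entry criteria admit ALT/AST up to <3×ULN and bilirubin up to 1.5×ULN; other outputs fill the gap only in part

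*SAP*

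**What the plan says.** Protocol 6.3, exclusion 16 (also in the synopsis), removes subjects whose Screening ALT or AST is 3×ULN or more, or who have "total bilirubin $> 1.5 \times$ ULN". Values above ULN but inside those limits do not bar entry.

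SAP 8.5 presents "The number and percentage (based on the number of subjects with a normal level at baseline) of subjects in each treatment group" with transaminases above 3×, 5× and 10×ULN. For bilirubin it adds "an elevated bilirubin level (> 1.5 × ULN and > 2 × ULN) will be presented by study visit". It plans no matching table for subjects abnormal at baseline and does not define a normal level.

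The same section plans other laboratory outputs without this restriction:
- shift tables of baseline grade against grade at each visit, using the modified DMID grades of Appendix 3;
- "Number and percentage of subjects with at least a 2-grade increase from baseline", with percentages over subjects who have both a baseline and a post-baseline evaluation, plus a listing;
- descriptive statistics by time point and for the worst post-baseline value;
- a Hy's law listing and listings of all laboratory data.

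**The concern.** The table's base is narrower than the population that is enrolled and dosed. A subject who enters at 2.0×ULN and reaches 10.1×ULN has crossed all three transaminase limits, yet on the restrictive reading is not counted in the one table built to show those limits. Subjects who start above ULN are also nearest to the limits.

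The hepatic signal matters here. On 200 mg iv for seven days, Protocol 7.4 says: "Alanine aminotransferase was reported as increased in 26% of subjects". Group 1 receives 200 mg iv on every treatment day. The same bullet calls that regimen safe and well tolerated and puts the ALT change at about 30 IU/L on the last infusion day, so this is a reason to report ALT completely, not evidence of harm. Safety is a secondary objective, and at about 40 subjects per arm one crossing is 1/40 = 2.5 percentage points.

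**Working it through.** The plan states no figure for this table, so there is nothing to reproduce. The check is which crossings the other summaries would catch.

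**Inputs.** Entry limits: Protocol exclusion 16. Table base and thresholds: SAP 8.5. Grades: SAP Appendix 3, in multiples of ULN.
- ALT/AST: Grade 0 <1.25; Grade 1 1.25–2.5; Grade 2 >2.5–5; Grade 3 >5–10; Grade 4 >10.
- Total bilirubin: Grade 0 <1.1; Grade 1 1.1–1.5; Grade 2 >1.5–2.5; Grade 3 >2.5–5; Grade 4 >5.

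I take normal to mean at or below ULN for that analyte.

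**Step 1: admitted but outside the base.** ALT/AST above 1 and below 3×ULN; bilirubin above 1 and up to 1.5×ULN.

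**Step 2: does the summary of rises of two or more grades catch them?** Rise = post-baseline grade − baseline grade.

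| ALT/AST baseline (×ULN) | Grade | Reaches >3 to 5 (Grade 2) | Reaches >5 to 10 (Grade 3) | Reaches >10 (Grade 4) |
|---|---|---|---|---|
| >1 to <1.25 | 0 | +2, caught | +3, caught | +4, caught |
| 1.25 to 2.5 | 1 | +1, missed | +2, caught | +3, caught |
| >2.5 to <3 | 2 | 0, missed | +1, missed | +2, caught |

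| Bilirubin baseline (×ULN) | Grade | Reaches >1.5 to 2.5 (Grade 2) | Reaches >2.5 to 5 (Grade 3) | Reaches >5 (Grade 4) |
|---|---|---|---|---|
| >1 to <1.1 | 0 | +2, caught | +3, caught | +4, caught |
| 1.1 to 1.5 | 1 | +1, missed | +2, caught | +3, caught |

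Examples of missed rises:
- ALT 1.3 to 4.9×ULN: Grade 1 to 2, and 4.9/1.3 = 3.8-fold.
- ALT 2.6 to 9.9×ULN: Grade 2 to 3, and 9.9/2.6 = 3.8-fold.
- Bilirubin 1.2 to 2.1×ULN: Grade 1 to 2.

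**Step 3: do the shift tables fill the rest?** They include every baseline grade, and 5× and 10×ULN for ALT/AST and 1.5×ULN for bilirubin are grade boundaries, so those crossings can be read off. ALT/AST 3×ULN and bilirubin 2×ULN both lie inside Grade 2 and cannot be. These are also cut-points in the SAP's Hy's law definition.

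**Step 4: the denominator-only reading.** If abnormal-baseline subjects stay in the numerator and leave the denominator, the percentage is the all-subject rate multiplied by 1/(1 − f), where f is the share abnormal at baseline. This gives 1/0.95 = 1.05, 1/0.90 = 1.11, 1/0.80 = 1.25 and 1/0.70 = 1.43 for f = 5%, 10%, 20% and 30%.

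**Step 5: how many subjects.** About 200 subjects over five equally allocated arms is 200/5 = 40 per arm. The documents do not give f. Under the assumed range, 0.05 × 40 = 2, 0.10 × 40 = 4, 0.20 × 40 = 8 and 0.30 × 40 = 12 per arm lie outside the base.

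**The case against.** The strongest reply is that little is hidden. A normal-baseline base is a recognised way to isolate new elevations: a move from 2.9 to 3.1×ULN crosses a limit with almost no change. The rule applies to every arm alike. The two-grade summary catches every crossing from a baseline just above ULN, every ALT/AST value above 5×ULN from a Grade 1 baseline and every value above 10×ULN from a Grade 2 baseline. Worst-value statistics include all these subjects. Protocol 12.6.1 also plans clinically notable laboratory summaries with no baseline limit, though SAP 8.5 ties these to Appendix 3 without naming a grade cut-off. The Hy's law listing is unrestricted, and clinically significant abnormalities are reported as adverse events.

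Most of this stands. A reader might infer that liver signals in these subjects vanish from the report; the outputs just listed show that they do not. What does not stand is that the outputs are equivalent. Listings and means are not counts per arm, and the Hy's law listing needs transaminase and bilirubin criteria at the same visit, so an isolated ALT rise does not enter it.

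A reader might also infer that the table distorts arm decisions, because SAP 3.4 says "Decisions on randomization re-allocation and/or dropping dose groups will be based primarily on safety and tolerability". The documents do not support that. SAP 3.5 places the SAP's analyses after the end of the study, and the interim reviews follow a DMC charter that is not among these documents. Nothing says that the DMC sees only this table.

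**Conclusion.** The point holds as a reporting gap in one table. On either reading, its percentages do not describe the dosed population: the restrictive reading omits the admitted abnormal-baseline subjects, and the denominator-only reading mismatches numerator and denominator. No planned table built on these limits or grades gives a complete per-arm count of ALT/AST >3×ULN or bilirubin >2×ULN among these subjects.

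The cells that the two-grade summary misses are ALT/AST baseline 1.25–2.5×ULN peaking at >3 to 5×ULN, ALT/AST baseline >2.5 to <3×ULN peaking at >3 to 10×ULN, and bilirubin baseline 1.1–1.5×ULN peaking at >1.5 to 2.5×ULN.

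The size rests on an assumed 5–30% abnormal at baseline, about 2–12 of 40 per arm. The documents give no crossing rates by baseline status, so no understated percentage can be calculated and none is claimed. The defect is the missing companion rows, not the normal-baseline view itself.

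**What to change.** In SAP 8.5, present the threshold counts and percentages for all Safety subjects with a baseline and a post-baseline value of that analyte. Under each, add one row for normal baseline and one for baseline above ULN, each with its own matching numerator and denominator. State that normal is judged per analyte as at or below ULN; Grade 0 in Appendix 3 runs higher, to <1.25×ULN for ALT/AST and <1.1×ULN for bilirubin. Multiples of baseline for the above-ULN row are optional.

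The cost is a wording change and a few rows in an existing table. The data are already collected, and the normal-baseline view is kept.
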